1. PURPOSE OF STUDY

This study represents the third phase of a larger research project developed for a U01 award as part of the Collaborative Initiative on Fetal Alcohol Spectrum Disorders (CIFASD) funded by the National Institute on Alcohol Abuse and Alcoholism (NIAAA). The overall project aims to develop and evaluate a mobile health (mHealth) application (app) for parents/caregivers of children with fetal alcohol spectrum disorders (FASD). The primary focus of the FMF Connect app is to provide parent/caregiver education and support.

The first phase of this project was approved under IRB protocol #1266 (legacy RSRB#67394). In that phase we used qualitative research methods to engage parents and caregivers in the development of the mHealth intervention and obtain iterative feedback on acceptability and feasibility. A prototype of the app was developed in both iOS and Android and beta-testing was completed with parents/caregivers and providers. In the second phase of the study, we conducted a feasibility trial of the FMF Connect app with parents/caregivers under IRB protocol #4433. This included quantitative pre-post surveys and qualitative interviews with a subsample of users to optimize the intervention and trial procedures. In this third phase, we will conduct a larger scale randomized controlled trial (RCT) to test the efficacy of the FMF Connect app for parents/caregivers of children with FASD. We hypothesize that participants who receive the FMF Connect app (with or without the additional Coaching Module) will have improve outcomes relative to the waitlist control group. We anticipate the Coaching Module will increase participant engagement and usage of the FMF Connect app. Finally, we hypothesize that parental attributions of behavior targeted by the FMF Connect app will mediate intervention effects on child behavior and parenting self-efficacy.

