19. DATA ANALYSIS PLAN

Aim 1: For the two intervention groups, compare patterns of app usage (i.e., frequency, duration, use of core components) that relate to greater improvements in child and caregiver outcomes. Assess whether FMF Connect + Coaching results in higher usage of the app relative to FMF Connect alone.

A series of Multiple Regression analyses will test how app usage (i.e., frequency, duration, content/components accessed) relates to change in outcomes (i.e., parenting efficacy, FASD knowledge, family needs, child behavior) over time, controlling for pre-intervention level of functioning. With a sample size of 100 (n=50 per intervention group) and assuming $\alpha = .05$, there will be power .80 to detect small/medium effects ($f^2=.10$), .94 to detect medium effects ($f^2=.15$), and power $> .99$ to detect large effects ($f^2=.35$).

Aim 2: Examine whether families randomized to the three study arms differ in outcomes.

Repeated Measures Analysis of Variance will test whether families randomized to FMF Connect groups demonstrate improved outcomes relative to the waitlist group at 12 weeks. Pairwise comparisons will test for differences among intervention groups to determine if coaching adds additional benefit. Assuming a correlation among repeated measures ranging from .3 to .5 ($\alpha = .05$), with a sample of 150 and 3 time points, there will be power between .87-.96 to detect a small/medium effect ($f=.175$) and $>.99$ to detect medium and large effects ($f=.25$ and $f=.40$).

Aim 3: Examine whether parental attributions of child misbehavior mediate intervention-related changes in parenting efficacy and child behavior.

Mediation analyses will test whether parental attribution mediates the effects of FMF Connect on parenting efficacy and child behavior, including baseline levels of the respective outcomes. Given a sample size of 150, there will be adequate power ($>.80$) to detect small/medium effects within the mediation models using the bias-corrected bootstrap method.

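### Aim 2 names no app-versus-waitlist contrast at 12 weeks; the three-arm repeated-measures ANOVA it does name, read naturally, cannot separate benefit of the app from benefit of coaching alone

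*Combined protocol and SAP*

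**What the plan says.** Section 1 (Purpose of Study) gives the hypothesis: "participants who receive the FMF Connect app (with or without the additional Coaching Module) will have improve outcomes relative to the waitlist control group". Section 4 sets three arms with equal allocation, and Section 5 aims for 150 caregivers with usable data, so 50 per arm.

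Section 19 words Aim 2 more broadly: "Examine whether families randomized to the three study arms differ in outcomes". The method sentence says that a repeated-measures ANOVA "will test whether families randomized to FMF Connect groups demonstrate improved outcomes relative to the waitlist group at 12 weeks". The one follow-up named is "Pairwise comparisons will test for differences among intervention groups to determine if coaching adds additional benefit". Power is quoted "with a sample of 150 and 3 time points", at alpha .05 and a correlation among repeated measures of .3 to .5, as .87 to .96 for f = .175 and above .99 for f = .25 and .40.

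Section 4 lists six primary outcomes. Going by scale names in the Section 9 schedule, only parenting self-efficacy and behaviour attributions are measured at 6 weeks. Child behaviour, FASD knowledge, family needs and self-care are measured at T1 and T3 only.

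**The concern.** The hypothesis has a direction (improvement), a comparator (waitlist) and a time (12 weeks). A three-arm repeated-measures ANOVA does not by itself give a test with those three features. The term usually read for efficacy is group by time, with 2 df when a scale has T1 and T3, and 4 df when it has all three visits. It asks whether any arms differ in their profile over time, in any direction.

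Two results could then be significant without supporting the hypothesis as stated: a benefit confined to the coached arm, and, for the two primary outcomes with T2 data, a 6-week difference that has gone by week 12. If the app works equally well in both arms, the F also spends degrees of freedom on questions the hypothesis does not ask. Because the deciding term is not named, the analyst could choose among several tests after seeing the data.

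**Working it through.** **Inputs.** 150 analysed, 50 per arm (Sections 4 and 5); alpha .05 and r = .3 to .5 (Section 19). Assumed here: SD 1 at each visit, equal correlations, sphericity, and an illustrative 12-week gain of d = 0.5 SD, since the plan gives no mean difference.

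**The plan's own figure.** For group by time with 3 arms and 3 visits, lambda = f² × 150 × 3/(1 − r) on F(4, 294). At f = .175, lambda = 19.69 (r = .3) and 27.56 (r = .5), giving power .958 and .994, not .87 and .96. The stated range is matched by f = .15 (.873 and .963), or by f = .175 with a nonsphericity correction of about .60 to .65. The values above .99 do reproduce. Which inputs were used is a separate question.

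**Which arms improve.** On T1-T3 change the variance is 2(1 − r). Arm means (d, d, 0) and (d, 0, 0) both have a mean squared spread of (2/9)d², so lambda = 150 × (2/9) × d²/[2(1 − r)] in both cases. At d = 0.5 this is 8.333/1.4 = 5.95 (r = .3) and 8.333/1.0 = 8.33 (r = .5). On F(2, 147) the rejection rate is .571 and .727. Simulation (20,000 trials, d = .49, r = .5) agrees:

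| Test | Both app arms gain | Coached arm only |
|---|---|---|
| 2-df F | .708 | .710 |
| 4-df F, linear | .597 | .597 |
| Pooled contrast | .805 | .290 |

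**A difference at week 6 only (scales with T2).** For both app arms at (0, d, 0) over time, lambda = 50 × (2/3) × (2/3) × d²/(1 − r) = 7.94 and 11.11. The 4-df F rejects .593 and .759 of the time, with no difference at week 12.

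**Power against the direct contrast, both app arms gaining 0.5 SD.** Contrast: lambda = d²/[2(1 − r)(1/100 + 1/50)] = 5.95 and 8.33 on F(1, 147).

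| Test | r = .3 | r = .5 | Loss in points |
|---|---|---|---|
| 1-df contrast | .679 | .818 | reference |
| 2-df F | .571 | .727 | 10.7 and 9.1 |
| 4-df F, linear | .460 | .617 | 21.9 and 20.1 |
| 4-df F, complete by T2 or only at T3 | .593 | .759 | 8.6 and 5.9 |

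**At the plan's effect size.** At f = .175 the F and the contrast have power .958 v .993 and .994 v .999 (4 df, linear), or .905 v .949 and .974 v .989 (2 df): losses of 0.6 to 4.5 points. Read as an interaction effect, f = .175 means a 12-week difference of .175/√[(2/3)(1/2)/9] = 0.91 SD (three visits, linear) or .175/√[(2/3)(1/2)/6] = 0.74 SD (two visits). At that size every test is near its ceiling.

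**Unequal gains (2-df F v pooled contrast, coached arm at 0.5 SD).** If app alone gains half: .449 v .444 (r = .3) and .593 v .576 (r = .5). If it gains a third: .464 v .366 and .610 v .481, so the F has more power.

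**Specificity of the pooled contrast.** If only the coached arm gains 0.5 SD, the pooled difference is 0.25 SD, lambda = .0625/.042 = 1.49 and .0625/.030 = 2.08, and it rejects .228 and .300 of the time.

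**The case against.** The strongest reply is that no sentence makes the omnibus F the deciding test. The method sentence itself gives direction, comparator and time, and a contrast within the fitted ANOVA would fit it. A reader might infer that the plan has committed to the omnibus test; the documents do not say so. This stands, and the point rests on a natural reading. It does not remove the problem, because the contrast is still unnamed and the power statement is an ANOVA f over three visits.

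A reader might also infer a general loss of 9 to 21 points. The documents do not support that. It needs equal gains in both app arms, an effect near 0.5 SD, and for the upper end a linear course on a scale with T2 data, which only two of the six primary outcomes have. Unequal gains are plausible on the plan's own terms, since Section 1 expects coaching to raise engagement and Aim 2 asks whether it adds benefit.

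Nor do the documents say that a result driven by coaching would be reported as efficacy of the app alone. The planned comparison of the two app arms, together with the arm means, would help show where a difference lies.

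Finally, pooling is one defensible choice among several. If Section 1 means that each app arm must beat waitlist, the pooled contrast does not test that, and neither does the omnibus F.

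**Conclusion.** The concern holds in this form: the trial's central efficacy question has no named test that matches it, and the test most naturally read from the text would reject equally often for benefit in both app arms and for benefit in the coached arm alone (57% to 73% at 0.5 SD, 2 df). That equality follows from the algebra and holds for any d. It is the main reason to act.

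The power loss is secondary and conditional. With equal gains near 0.5 SD it is about 9 to 11 points for scales with T1 and T3, and about 6 to 9 (effect complete by T2 or only at T3) up to 20 to 22 (linear) for scales with three visits. It is about 1 to 5 points at f = .175. Against the 2-df F it is nil when app alone gains half as much as the coached arm, and it reverses at a third. The figures assume 50 analysed per arm, equal variances, r between .3 and .5, and sphericity.

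**What to change.** In Section 19, Aim 2, for each outcome:

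- Name as the efficacy test a two-sided 1-df contrast at T3 from the same fitted model, accounting for baseline: the mean of the two app arms minus waitlist.
- Plan alongside it coached minus app alone, and each app arm against waitlist, each with estimate, confidence interval and test.
- State that efficacy of the app without coaching is claimed only if its own comparison with waitlist supports it.
- State that the omnibus group-by-time F is not the efficacy test.
- Say whether the phrase in Section 1 about the app with or without coaching means the average of the two arms or each arm separately.

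The cost is wording only: no extra participants, visits or measures. The downside is that the pooled contrast loses power if the two arms gain very unequally, and it still rejects 23% to 30% of the time when only the coached arm gains 0.5 SD. The arm-specific comparisons are needed for that reason, and they are less powerful: with 50 v 50, each has about 68% power where the pooled contrast has 80%.

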4. STUDY DESIGN

This study involves a three arm RCT with equal allocation to the following conditions: (1) FMF Connect + coaching, (2) FMF Connect alone, and (3) waitlist control. Quantitative survey data will be collected at three timepoints: baseline (T1), 6-weeks (T2), and 12-weeks (T3). The T2 timepoint will involve an abbreviated battery designed to allow statistical tests of mediation hypotheses (see Data Analysis Plan below). Primary study outcomes include child behavior, parent FASD knowledge,

parenting self-efficacy, behavior attributions, family needs met, and parent use of self-care. We are also interested in participant ratings of app quality and patterns of app usage. App usage will be recorded through AWS during the study period. After T3, study participants in the waitlist control group will receive the FMF Connect app.

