5. SUBJECT POPULATION

The subject population will include parents and caregivers of children (ages 3-12) with fetal alcohol spectrum disorders (FASD) or affected by prenatal alcohol exposure (PAE) who live in the United States.

We are aiming to include 150 parents or caregivers with usable data in this study to achieve adequate power for study aims (see data analysis section below). We expect a portion of families will enroll in the study, but not complete assessments or install the app. Based on our feasibility trial, 57% of participants who initiated screening were eligible for the study and had complete data. This percentage may be a bit lower than we can achieve for the proposed RCT given that the COVID-19 pandemic began right after the initiation of the feasibility trial and affected participation. We also identified some inefficiencies in our enrollment process that we can improve to reduce incomplete data. Of eligible families selected for the study, we expect about 85% of eligible families to complete baseline surveys. Of these families, about 80% are likely to install and use the app at least once. To attain our desired sample size, we will aim to enroll about 300 parents and caregivers.

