9. STUDY PROCEDURES

Data Collection & Randomization Procedures

Parents/caregivers who are eligible for the study will be sent an email inviting them to complete the baseline study surveys (see survey battery below) administered by REDCap. Participants will be

asked to enter their zip code to verify their identity when completing baseline and follow-up surveys (this will be verified against value entered in demographic surveys in the screening module). Families deemed ineligible after detailed review will be informed of their status.

Following baseline survey completion, participants will be randomized to one of three arms of the RCT:

1. FMF Connect app + text based coaching (within the app)
2. FMF Connect app (without coaching)
3. Waitlist control

Randomization will occur through the REDCap Randomization module, with an equal allocation pattern across groups. Participants will be notified of their group status via email. Emails for parents/caregivers in either of the FMF Connect app intervention groups (groups 1 and 2) will also include instructions of how to install the FMF Connect app on their devices. The email for the parents/caregivers in the FMF Connect app + coaching group (group 1) will inform them that they will receive an introductory email from their assigned coach in the next few days. Details about the FMF Connect app and Coaching interventions and described below.

All participants regardless of group assignment will receive emails through REDCap at 6 weeks and 12 weeks inviting them to complete follow-up surveys, along with a personalized link (see survey battery below). The assessment battery is estimated to take 35-45 minutes to complete at T1 and T3; T2 is estimated at 15-20 min. Waitlist control participants will receive the FMF Connect app following T3 survey completion.

Measure	Baseline (T1)	6-Weeks (T2)	12-Weeks (T3)
Eyberg Child Behavior Inventory (5-8min)	X		X
Reasons for Children’s Behavior Scale (4-6min)	X	X	X
Everyday Life Scale (4-6min)	X	X	X
Parenting Sense of Competence Scale (3-5min)	X	X	X
Family Needs Questionnaire (3-5min)	X		X
Knowledge & Advocacy Questionnaire (15-20min)	X		X
Self-Care and Support Assessment (3-5min)	X		X
Adverse Childhood Experiences (2 min)	X		
Family Background & Services Survey (5-10min)	X		X
COVID-19 Experiences Survey (5 min)			X
User Version of the Mobile Health Application Rating Scale (5-8min)			X

FMF Connect mHealth Intervention

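### The Aim 2 power range of .87-.96 does not follow from its printed inputs, and its three time points do not fit four of the six primary outcomes

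*Combined protocol and SAP*

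**What the plan says.** Section 19, Aim 2, plans a repeated measures analysis of variance comparing the arms at 12 weeks. Its power statement begins "Assuming a correlation among repeated measures ranging from .3 to .5" at alpha .05 and continues "with a sample of 150 and 3 time points, there will be power between .87-.96 to detect a small/medium effect ($f=.175". It then claims power above .99 at f=.25 and f=.40. It does not name the term tested (group-by-time or a main effect), and it gives no epsilon for departure from sphericity.

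Section 4 describes three arms with equal allocation and six primary outcomes: "Primary study outcomes include child behavior, parent FASD knowledge", and then "parenting self-efficacy, behavior attributions, family needs met, and parent use of self-care". On the 6-week visit it says: "The T2 timepoint will involve an abbreviated battery designed to allow statistical tests of mediation hypotheses". Section 5 bases the sample size on the analysis section: "We are aiming to include 150 parents or caregivers with usable data in this study to achieve adequate power for study aims".

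The measure table in section 9 marks four instruments at T1 and T3 only: "Eyberg Child Behavior Inventory (5-8min)", "Knowledge & Advocacy Questionnaire (15-20min)", the Family Needs Questionnaire and the Self-Care and Support Assessment. The Reasons for Children's Behavior Scale and the Parenting Sense of Competence Scale are marked at all three visits.

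**The concern.** This sentence is the only power justification for the efficacy aim, so a reader should be able to recover its result from its inputs. Two things stand in the way. The printed range is lower than the stated inputs give for the natural test of the hypothesis, by more than rounding can explain. And the number of time points describes a design that most of the primary outcomes do not have.

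What is at stake is knowing which effect size and which assumptions the 150 were planned on. Depending on the answer, the true power of the planned test lies above or below the printed figure.

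**Working it through.** **Inputs.** From section 19: N=150, m=3 time points, f=.175, r=.3 to .5, alpha=.05. From section 4: k=3 arms, equal allocation. Section 5 says that the 150 have usable data, so no dropout factor is applied. Not stated: the tested term and epsilon (ε). I take ε=1 (sphericity) first.

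**Group-by-time test.** Noncentral F with λ = ε·f²·N·m/(1−r), df1 = ε(k−1)(m−1), df2 = ε(N−k)(m−1).

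At the printed inputs, df = 4 and 294, with critical F = 2.402:
- r=.3: λ = .030625 × 150 × 3 / .7 = 19.69, power .958 (printed .87)
- r=.5: λ = .030625 × 150 × 3 / .5 = 27.56, power .994 (printed .96)

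The gaps are 8.8 and 3.4 percentage points.

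**Main effects at the same inputs.**
- Time (λ as above, df 2 and 294): .983/.998. No ε from .50 to 1 brings this to .87/.96.
- Arm (λ = f²Nm/[1+(m−1)r], df 2 and 147): λ = 8.61/6.89, power .742/.639. This falls as r rises. At f=.25 it gives .969/.924, which conflicts with the printed claim of more than .99.

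The group-by-time test does reproduce the claims above .99: at f=.25 and f=.40 it gives at least .9998 with three time points and at least .9976 with two. The mismatch is therefore confined to the f=.175 figure, and group-by-time is the most plausible intended term.

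**What would reproduce .87/.96 for group-by-time (r=.3/.5).**

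| Change from the printed inputs | Power |
|---|---|
| f=.15, sphericity, 3 time points | .873/.963 |
| f=.175, ε=.64 | .869/.960 |
| f=.175, ε=.65 | .873/.962 |
| f=.175, N=110, 3 time points | .870/.962 |
| f=.175, N=135, 2 time points | .870/.958 |

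These are numerical matches only. No section shows that any of them was used.

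**Time points by outcome.** Matching outcomes to instruments by name (the protocol gives no explicit mapping), child behavior, FASD knowledge, family needs and self-care are measured twice. Attributions and parenting self-efficacy are measured three times. For the first four, m=2, df = 2 and 147, critical F = 3.058, and ε has no role.

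| N=150, group-by-time, r=.3/.5 | 3 time points, ε=1 | 2 time points |
|---|---|---|
| f=.175 | .958/.994 | .905/.974 |
| f=.15 | .873/.963 | .792/.913 |

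**Sensitivity to ε at f=.175, 3 time points.** ε=.63 gives .865/.957, ε=.60 gives .852/.950, and the lower bound ε=.50 gives .800/.919. Below about .63 the result falls under the printed range.

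**The case against.** The strongest reply is that the printed range errs on the safe side and so does no harm. At f=.175 the recomputed power is above it with three time points and with two. That stands for the group-by-time test under sphericity. It does not stand without those conditions, because section 19 states neither the term nor an epsilon. It reverses for the twice-measured outcomes if f=.15 was the real input, and for the outcomes measured three times if epsilon is low.

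A second reply is that the reduced 6-week battery is disclosed in section 4 and tabulated in section 9, and that three time points is correct for the study and for two primary outcomes. This is fair: nothing is hidden, and at f=.175 two time points still give .90-.97. What remains is that the sentence draws no distinction between outcomes, and no three-time-point figure applies to four of the six.

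A third reply is that an epsilon was used and simply not printed. That is possible, but it is one of several explanations that fit equally well, and it could not carry over to outcomes measured twice.

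A reader might also infer that f was mistyped for .15. The documents do not support choosing that explanation over a different epsilon or a different N.

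**Conclusion.** The point holds, as a minor one. The printed .87-.96 is not the power that the printed inputs give: for group-by-time under sphericity it should be .96-.99, and neither main effect fits. The three-time-point premise does not match the schedule for four of the six primary outcomes, on a match of outcomes to instruments by name.

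The direction of the error is conditional. For group-by-time under sphericity at f=.175 the printed range is conservative (.96-.99 with three time points, .90-.97 with two). It is optimistic for the twice-measured outcomes if f=.15 was used (.79-.91), and for the outcomes measured three times if epsilon is below about .63 (.80-.92 at epsilon .50).

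A reader might infer that the trial is underpowered. The documents do not support that: at the printed effect size under sphericity, power is at least .90 on either schedule, and the claims above .99 at the larger effects reproduce. Nothing here shows that N=150 is inadequate.

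**What to change.** Restate the Aim 2 power sentence with the inputs actually used: tested term, f, N, number of time points and epsilon. Print the power that goes with them, with a separate line for the outcomes measured at T1 and T3 only.

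- If the test is group-by-time at f=.175 under sphericity: .96-.99 for outcomes measured three times, .90-.97 for those measured twice.
- If f=.15 was used, again under sphericity: .87-.96 and .79-.91.
- If an epsilon below 1 or a different N was used: state it and print the matching figures.

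The cost is wording only, with no extra participants and no change to the design or analysis.

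### The Aim 2 power statement does not name the effect it powers, its f and its power do not match, and its small/medium label fits neither f on the only between-arm test with power that high

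*Combined protocol and SAP*

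**What the plan says.** Section 19, Aim 2, gives the analysis as follows: "Repeated Measures Analysis of Variance will test whether families randomized to FMF Connect groups demonstrate improved outcomes relative to the waitlist group at 12 weeks". The power statement that follows has these inputs: "Assuming a correlation among repeated measures ranging from .3 to .5", alpha .05, "with a sample of 150 and 3 time points". Its result is "there will be power between .87-.96 to detect a small/medium effect", with that effect set at f=.175, and power above .99 for effects labelled medium (f=.25) and large (f=.40). The section does not say whether the powered effect is group, time or group-by-time. It does not turn f into a difference between arms.

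Section 5 rests the sample size on this section; it aims for "150 parents or caregivers with usable data in this study to achieve adequate power for study aims".

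Section 4 sets three equal arms, so 50 per arm. The measures table in section 9 gives the Eyberg inventory (child behavior) at T1 and T3 only. The family needs, knowledge and self-care instruments follow the same schedule. The stated three time points therefore do not apply to several of the outcomes that section 4 calls primary.

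**The concern.** The values .175, .25 and .40, with labels running from small/medium to large, carry their usual meaning when f describes the spread of arm means at one time point. In a group-by-time test, f is the root mean square of the interaction cell deviations divided by the outcome SD. One difference between arms is spread over every arm-by-time cell, so the same f stands for a much bigger difference.

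A reader who takes the label at face value will believe that 150 families give about 90% power for a modest benefit of the app. That reader could then give a null result more weight against such a benefit than the design supports.

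**Working it through.** **Inputs.** From the protocol: N=150, k=3 equal arms, m=3 time points (m=2 for T1/T3 scales), r=.3 to .5, alpha=.05, f=.175. Assumed here: equal correlation between all pairs of time points, and effects measured in single-time-point SDs.

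**1. The printed power.** Noncentral F, with f²Nm = .030625 × 450 = 13.78.
- Group-by-time: λ = f²Nm/(1−r), df 4 and 294. λ = 19.69 and 27.56, so power is .958 (r=.3) and .994 (r=.5).
- Between-arm main effect: λ = f²Nm/(1+(m−1)r), df 2 and 147. λ = 8.61 and 6.89, so power is .742 and .639.
- Time main effect: power .983 and .998, but it compares no arms.
- Group-by-time with m=2: power .905 and .974.
- Group-by-time with f=.15, m=3: .0225 × 450 = 10.125, λ = 14.46 and 20.25, power .873 and .963.

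Only the last line gives the printed .87-.96. At f=.25 the between-arm test gives .97 and .92, which also falls short of the printed >.99.

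**2. What f means as an arm difference.** Let both app arms gain d over waitlist. The interaction f is d × (SD of the arm pattern) × (SD of the time pattern). The arm pattern (1, 1, 0) has SD √(2/9) = .4714.

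| Time course | SD of time pattern | f per unit d | d at f=.175 | d at f=.15 |
|---|---|---|---|---|
| T1, T3 only | .5000 | .2357 | 0.74 | 0.64 |
| Three times, step | .4714 | .2222 | 0.79 | 0.67 |
| Three times, linear | .4082 | .1925 | 0.91 | 0.78 |

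On the same scale the f=.25 labelled medium is 1.06 to 1.30 SD. At a single time point, f=.175 is .175/.4714 = 0.37 SD.

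**3. Where the omnibus test reaches 80% power.** The λ needed is about 9.8 (df 2, 147) or 12.1 (df 4, 294), and d = √(λ(1−r)/(Nm)) divided by the f per unit d. For r=.3 and .5:
- T1, T3 only: 0.64 and 0.54 SD
- three times, step: 0.62 and 0.52 SD
- three times, linear: 0.71 and 0.60 SD

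**4. Power at 0.37 SD.**

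| Test | r=.3 | r=.5 |
|---|---|---|
| Omnibus group-by-time, T1/T3 only | .34 | .46 |
| Omnibus group-by-time, three times, step | .34 | .47 |
| Omnibus group-by-time, three times, linear | .26 | .36 |
| Pooled app (100) v waitlist (50), change score | .43 | .56 |
| Pooled app (100) v waitlist (50), baseline-adjusted | .60 | .69 |

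The pooled rows use SE = SD × √(1/100 + 1/50) = SD × .1732. The SD is √(2(1−r)) = 1.18 or 1.00 for change, and √(1−r²) = .954 or .866 with adjustment. Simulation of the omnibus test (4,000 replicates per case) gave .26 to .48.

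**5. 80% power for the pooled contrast, two-sided .05.** About 2.80 × SE, slightly more with the t distribution: 0.58 SD (r=.3) and 0.49 SD (r=.5) on change; 0.47 and 0.42 SD with baseline adjustment.

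**The case against.** A reader might infer that 150 families are enough only for a large difference. The documents do not support that. The 0.74-0.91 SD values are differences that the group-by-time test would detect with power of .90 or more, not the smallest that it can find. The omnibus test reaches 80% power at 0.52-0.71 SD, and the pooled contrast at 0.42-0.58 SD.

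It is also fair to say that 0.37 SD is a convention. The protocol never defines small/medium in SD units and sets no target difference. The 0.37 figure is only what the printed f would mean between three arms at one time point. It serves here as a yardstick for the label.

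The test is inferred from a printed power that does not match the printed f, so the sponsor may have used f=.15. If so, the implied difference is 0.64-0.78 SD. That changes the size of the point but leaves it standing.

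Lastly, the omnibus figures are the low end for the question that Aim 2 asks, which is app versus waitlist at 12 weeks. A focused contrast does better. At 0.37 SD it still gives .43-.69, below both .80 and the printed range.

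**Conclusion.** The power statement is wrong as written in two ways. The printed f and power do not belong together on any test that compares arms: group-by-time gives .96-.99 at f=.175, and .87-.96 belongs to f=.15. The label also misdescribes the effect. On the group-by-time test f=.175 is 0.79-0.91 SD with the stated three time points and 0.74 SD for T1/T3 scales, about twice or more the 0.37 SD that the same f means between arms at one time point. At 0.37 SD every test considered falls below the printed range.

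The SD figures assume that both app arms gain equally (gain in one arm only gives the same values), equal correlations of .3 to .5, and 150 families with usable data. A graded response across the arms would need 0.86-1.05 SD between the extreme arms to give f=.175. The finding concerns what the power statement claims; it does not show that the sample size is inadequate.

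**What to change.** In section 19, Aim 2:
- name the ANOVA effect being powered;
- reconcile f with the printed power;
- drop the small/medium label;
- state the detectable 12-week difference between arms in SD, with the assumed response pattern and correlation, separately for outcomes measured at two and at three time points.

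Possible wording for the main comparison: with 100 app and 50 waitlist families, two-sided alpha .05 and a correlation of .5 to .3, 80% power is reached at a difference of 0.42-0.47 SD with baseline adjustment, or 0.49-0.58 SD on change scores. If the omnibus group-by-time test is kept, give its own figure, about 0.52-0.71 SD. Section 5 can then refer to the restated figures.

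The cost is protocol wording and a less favourable stated power. No design change is needed.
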